1.1. Assessment and management of risk

Electrical stimulation is currently being used in routine care physiotherapy practice with minimal reports of adverse events. Electrical stimulation has been incorporated into best practice guidelines for people with stroke as well as people with Multiple Sclerosis. The risk associated with using electrical stimulation within this study is not different to using electrical stimulation within routine clinical practice.

Previous study of electrical stimulation report few adverse events. Common adverse events when they occur are skin irritation at the electrode site, muscle fatigue and soreness following electrical stimulation and joint pain.

Participants will be instructed to let the research team know if they experience any adverse events, these will be monitored as per Section 8 Safety Measures. If participants experience muscle soreness, muscle fatigue, joint pain, or skin irritation they will be supported by the research team to manage this to be able to continue in the study.

The benefits of using electrical stimulation are maintaining muscle bulk and size which will help to prevent atrophy, improved circulation at the stimulation site, and the time doing the stimulation will contribute to additional minutes of exercise which is recommended in the new Clinical Stroke Guidelines.

2. OBJECTIVES AND OUTCOME MEASURES/ENDPOINTS 2.1. Primary objective

The primary aims of this feasibility study are to i. assess the feasibility and acceptability of SNMES started within 2-weeks after stroke and applied for 12-weeks to the weakened lower limb muscles and ii.to provide necessary data to inform the design of a future definitive RCT testing whether SNMES started within two weeks after stroke prevents muscle wastage and improves recovery of strength, walking and quality of life in people with severe lower extremity weakness.

The primary feasibility and acceptability objectives are described below.

- 1. Determine the feasibility and acceptability of the SNMES intervention started within 2-weeks in people after stroke.
- 2. Estimate screening, recruitment and attrition rates, and reasons for declining participation or leaving the study early (where possible).
- 3. Estimate adherence/engagement to the SNMES protocol, including number of sessions completed/total sessions in treatment protocol

STIM-STROKE Protocol v1.0 30-04-2025

IRAS ID: 332116 Page **17** of **70**

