Stroke teams manage issues relating to capacity on a frequent basis and are therefore typically very aware of the principles of the Mental Capacity Act, capacity assessments and informed consent.

Process if a participant with stroke loses capacity during the study

Although unlikely, a participant who gave informed consent at the point of recruitment, may lose capacity during the course of the study. It is likely that any loss of capacity at this stage reflects medical instability - such as a further stroke, infection, or other medical event.

The study will adhere to the principles, as laid out and defined in the Mental Capacity Act (2005). At the time of the person consenting to the trial, they have expressed a wish to participate. Therefore, the person will remain in the study, as long as it is appropriate clinically, and there is no observable or communicated evidence that they do not wish to continue.

If the individual has had a change in medical status is communicating that they do not wish to continue in the trial, or are demonstrating an unwillingness to participate in any of the trial interventions (e.g. electrical stimulation or assessments), then the trial intervention/follow-up would be paused for 7 days. Furthermore, participants that have a change in medical status during the trial will have the trial interventions (e.g. SNMES) and follow up assessments

STIM-STROKE Protocol v1.0 30-04-2025

IRAS ID: 332116 Page **36** of **70**

paused for up to 7 days (less if medical status improves sooner). During this time the research team and clinical team will monitor the participants medical situation and a member of the research team will re-evaluate if they are stable to continue with the trial with the following outcomes:

- Participants who are medically stable and want to continue will continue with the trial.
- Participants that are medically stable but do not want to continue with the trial will be withdrawn.
- If the participant is identified to not be medically or neurologically stable irrespective
 of capacity the person will not be clinically appropriate to remain in the trial and will
 be withdrawn.

Consent process for clinicians

Clinicians who have been involved in supporting participants in the study will be invited to take part in a focus group discussion with other clinicians at the end of the intervention period. Clinicians will have an opportunity to decide if they would like to take part and have all their questions answered.

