6.5. Responsibilities

Process for SAE

- 1. SAE identified
- 2. SAE CRF completed by a member of the research team
- 3. SAE CRF is sent to the local PI
- 4. Local PI will assess SAE for severity and causality and notify the CI of the SAE
- 5. The Sponsor will be made aware of the SAE within 24 hours of knowledge of the event via a member of the research team

Research practitioner

- Collecting data at study visit (Visit 2, 3, 4) regarding AE, AR, and SAE
- Reporting any AE, AR, SAE on the respective CRF
- Sending SAE CRF to local PI for evaluation

Principal Investigator (PI):

- Checking for SAEs when participants attend the study visit.
- Using medical judgement in assigning seriousness and causality.
- Ensuring that all SUSARs are recorded and reported to the sponsor within 24 hours of becoming aware of the event and provide further follow-up information as soon as available
- Ensuring that SUSARs are chased with Sponsor if a record of receipt is not received within 2 working days of initial reporting.

Chief Investigator (CI):

- Clinical oversight of the safety of study participants, including an on-going review of the risk / benefit.
- Immediate review of all SUSARs.

Sponsor:

- Central data collection and verification of adverse events according to the trial protocol onto a database.
- Using medical judgement to assign the SAE's seriousness and causality where it has not been possible to obtain local medical assessment – UHD Clinical Director for Research.
- Reporting safety information to Research Steering Group.
- Expedited reporting of SUSARs to the REC within required timelines.

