7.3. Statistical analysis plan

Quantitative data

A detailed statistical analysis plan (SAP) will be drafted by the trial statistician and the trial will be reported in accordance with the CONSORT 2010 statement extension to pilot and feasibility trials.⁴⁸

STIM-STROKE Protocol v1.0 30-04-2025

IRAS ID: 332116 Page **54** of **70**

No statistical comparisons between treatment groups will be undertaken on baseline or follow-up data as the trial is not designed to test effectiveness. Iinstead the focus will be on presenting summary statistics with appropriate confidence intervals, to meet listed study objectives.

The flow of participants through the study will be presented in a CONSORT-style diagram with reasons for discontinuation or withdrawal given where available. Descriptive statistics will be reported for the feasibility outcomes: recruitment, retention rate, adherence rates, quality of data collection, intervention delivery and fidelity. Additionally, descriptive statistics will be used to describe the outcome measures collected at Visits 1-4.

Data will inform a potential definitive study with variability in candidate primary and secondary measures calculated to inform size (power calculation) for the definitive trial.

Adverse events will be summarised descriptively.

Data management will be undertaken using REDCap and Microsoft Excel. Statistical analysis will be undertaken using STATA version 16 or later, supplemented where required by R.

Qualitative and quantitative data will be used in combination to inform the future definitive trial design. The intervention and methodology will also be iteratively mapped to the TIDieR checklist, APPEASE framework and Health Inequalities Assessment toolkit.

Qualitative data

Interviews/focus groups will be recorded and transcribed verbatim using an approved transcription service that complies with GDPR. All identifying features of the recording and transcription will be anonymised.

Thematic analysis using the framework method will be used to explore common themes taking a deductive approach and considering emergent themes involving inter-researcher and PPI interpretation ^{44,49} Data management and data analysis may be undertaken using NVivo software.

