New Joint pain	Musculoskeletal system	Participant and health care team education on joint pain signs and symptoms. Participants will be instructed to report any new joint pain to the research team. The research team will assess the joint pain and act accordingly to the participants symptoms, for example, reducing the intensity of the stimulation.	Healthcare team education session. Initial session of SNMES, check at Visit 2 (week 6) and Visit 3 (week 12)
Pain at stimulation site	Neuromuscular System	Participants and the healthcare team will receive education on recognising signs and symptoms of pain at the site of stimulation. Participants will be instructed to report any pain at the stimulation site to the research team, who will act accordingly to the participants' symptoms. For example, reducing the intensity of the stimulation reducing muscle workload, changing the electrodes, or using larger electrodes.	Healthcare team education session. Initial session of SNMES, check at Visit 2 (week 6) and Visit 3 (week 12)

The research and clinical teams will be educated in the potential risks associated with electrical stimulation as well as how to mitigate the risk and when to refer on for additional assessment or treatment. Participants and their caregivers will also be educated on the potential risks associated with electrical stimulation and instructed to contact a member of the research team as soon as something is not right.

IRAS ID: 332116 Page **69** of **70**

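### The only scheduled checks for serious adverse events depend on an attended visit, so events in people who miss visits or are withdrawn may go unrecorded

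*Protocol*

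**What the plan says.** Protocol section 6.5 names two routine SAE checks. The research practitioner is responsible for "Collecting data at study visit (Visit 2, 3, 4) regarding AE, AR, and SAE", and the principal investigator for "Checking for SAEs when participants attend the study visit". The SAE process in the same section starts once an event has been identified. Its clock runs from awareness: "The Sponsor will be made aware of the SAE within 24 hours of knowledge". It does not say how an event is identified between visits or without one.

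Events can also become known in other ways:
- Section 1.1: "Participants will be instructed to let the research team know if they experience any adverse events".
- Appendix 1: participants and caregivers are "instructed to contact a member of the research team as soon as something is not right", in a paragraph about the risks of electrical stimulation.
- Section 5.2.1.2, on loss of capacity during the study: after a change in medical status, intervention and assessments are paused for up to 7 days. "During this time the research team and clinical team will monitor the participants medical situation". If the participant is then still unstable, "the person will not be clinically appropriate to remain in the trial", and withdrawal follows.
- Section 5.9: participant and next of kin must be pursued before loss to follow-up is accepted. From people who withdraw, the data named are the primary outcome data.

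On analysis, section 7.3 says: "Adverse events will be summarised descriptively".

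**The concern.** Both scheduled checks require the participant to be seen. This population is within two weeks of a stroke, has severe leg weakness and cannot walk or transfer independently. The events that count as serious here, such as death, further stroke or readmission, are also reasons why a visit does not happen. Missing a safety check is therefore likely to be related to having had an event.

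Tracking adverse events is part of the first feasibility and acceptability outcome in section 2.3, and the results are meant to inform a definitive trial. If nobody records whether a non-attender's status was checked, the final summary cannot distinguish a participant without an SAE from one about whom nobody asked. A statistical analysis plan cannot repair this, because it cannot recover events that were never sought.

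**Working it through.** The protocol gives no SAE rate, SAE count or safety sample size, so there is no figure to reproduce. The check has three parts.

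**1. Is any SAE enquiry scheduled for someone who does not attend?**
- Section 6.5: both duties are tied to visits.
- Section 5.9: tracing serves retention and does not ask for events. SAEs are not among the data named for people who withdraw.
- Section 8.1: medical notes are named as a source for baseline data and medical history, not for SAEs.
- Section 5.2.1.2: monitoring covers the pause. Nothing is described after withdrawal. In contrast, section 6.2 states that follow-up data continue when SNMES is stopped for pregnancy.
- Section 1.1: reported events are to be monitored under a safety section numbered 8. Section 8 is data management, and safety is section 6.

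No scheduled enquiry was found for a missed visit or after withdrawal.

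A pause can itself cost a visit. The Visit 2 window is ±3 days, which is seven days inclusive. A full 7-day pause that begins inside the window, before the assessment has been done, uses up what remains of it.

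**2. How many people could be exposed?** Inputs are n = 60 (section 7.1) and the Table 3 limits for incomplete 6-month follow-up. I assume that incomplete means Visit 4 did not take place.
- Green, below 20%: at most 11/60 = 18.3%.
- Lower amber limit: 0.20 × 60 = 12.
- Upper amber limit: 0.40 × 60 = 24.

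The exposed time runs from the last attended visit. For someone last seen at Visit 3 it is about 26 − 12 = 14 weeks. Events before Visits 2 and 3 were already asked about if those visits were attended.

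**3. Can the shortfall be sized?** For one interval, let m be the share not attending, a and b the SAE risks in attenders and non-attenders, and s the share of non-attenders' SAEs that become known by other routes.
- Expected participants with an SAE = 60[(1 − m)a + mb]
- Recorded = 60[(1 − m)a + mbs]

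The values of a, b and s below are assumptions; none is in the protocol.

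| m | a | b | Expected | Recorded, s = 0 | s = 0.5 | s = 0.9 |
|---|---|---|---|---|---|---|
| 0.20 | 0.10 | 0.10 | 4.8 + 1.2 = 6.0 | 4.8 (80%) | 5.4 (90%) | 5.9 (98%) |
| 0.20 | 0.10 | 0.50 | 4.8 + 6.0 = 10.8 | 4.8 (44%) | 7.8 (72%) | 10.2 (94%) |
| 0.40 | 0.10 | 0.50 | 3.6 + 12.0 = 15.6 | 3.6 (23%) | 9.6 (62%) | 14.4 (92%) |

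The s = 0 column is a limit only, since the protocol does provide other routes. The shortfall, 60mb(1 − s), is never negative, so recording is too low whenever s is below 1. Its size depends mostly on s, which the protocol does not fix.

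**The case against.** A reader might infer from section 6.5 that SAEs can be found only at visits. The documents do not support that. Participants are told to report events at any time, caregivers are told to make contact, and reporting runs from knowledge of the event. Section 5 allows assessment at the place of residence for people who cannot walk or are hoisted, so some of the most disabled need not travel. Section 8.3 places the site principal investigators in the direct healthcare team. Contact with next of kin under section 5.9 would probably reveal most deaths. For someone withdrawn as unstable, the event that led to withdrawal is already known to the team, and only later events are at issue. All of this stands and limits the gap.

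A reader might also infer that SNMES will look safer than it is, because withdrawals could be more common in that arm. That is speculative. Failure to adhere, listed in section 5.9, may mean stopping the intervention without leaving the study. The SNMES arm also has more unscheduled contact (diary, device support, and the stimulation-risk education and checks in Appendix 1), which could raise its recorded events instead.

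Finally, the consequence is limited. Adverse events are only described, section 7.3 rules out comparing the arms statistically, and no Table 3 criterion uses SAEs. Sponsor procedures (section 6.4) and the monitoring plan (section 9) are not shown and may add checks.

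These points do not remove the gap. Self-report fails for those who die and is weak for those lacking capacity, whom the trial enrols. The caregiver instruction concerns stimulation risks. No route in the protocol is a scheduled question about serious events.

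**Conclusion.** The concern holds in a limited form. The only scheduled SAE checks depend on an attended visit. After a missed visit or withdrawal, detection of events since the last attended visit relies on unscheduled reports and on tracing that does not ask for events. Because serious events are themselves reasons for missing visits, SAEs may be under-recorded.

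This is a risk of under-recording and not a demonstrated bias. If capture outside visits is incomplete, the overall direction is downward. The amount cannot be derived from the protocol, and neither can the direction between arms. The exposure figures of 12 and 24 participants rest on Table 3's limits and on reading incomplete follow-up as no Visit 4. The percentages in the table rest wholly on assumed risks and should not be cited as an estimate. The gap is a matter of data collection fixed in the protocol, and it is cheap to close.

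**What to change.** In section 6.5, replace the attendance condition with an SAE check at each scheduled visit date (6 weeks, 12 weeks, 6 months) for every randomised participant, whether or not the visit takes place. The check is made in the hospital record or by asking the participant, next of kin or care provider. State that it continues after SNMES is stopped or visits end, unless the participant or consultee refuses. Record at each date whether status was ascertained, so that SAE counts can be reported with that denominator. Correct the cross-reference in section 1.1 so that it points to section 6.

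The cost is small: a short record check or call for those who miss a visit. Section 5.1 says that the staff who screen already have routine access to patient data, and section 5.9 already requires contact with next of kin. The one real demand is that participant and consultee consent wording must permit the check after withdrawal from visits, which should be settled with the ethics committee. The change concerns only how events are found and alters no clinical management.

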6.6. Final Report

A final report on the research will be submitted to the REC within 12 months of the end of the study.

6.7. Urgent Safety Measures

The CI may take urgent safety measures to ensure the safety and protection of the clinical trial subjects from any immediate hazard to their health and safety.

STIM-STROKE Protocol v1.0 30-04-2025

IRAS ID: 332116 Page **53** of **70**

The measures should be taken immediately. In the event of an urgent safety measure, regulatory approval is not required prior to implementation, however, it is the responsibility of the CI to inform the sponsor and Research Ethics Committee (via telephone) of this event immediately.

The CI has an obligation to inform both the Ethics Committee in writing within 3 days, in the form of a substantial amendment. The Sponsor must be sent a copy of the correspondence with regards to this matter.

7. STATISTICS AND DATA ANALYSIS

7.1. Sample size calculation

Quantitative Sample Size

We intend to recruit 60 participants with stroke over 12-months across two hospital sites, with a 2-month contingency if needed. Sample size estimation is based on feasibility parameters of recruitment uptake to a 10% margin of error for 90% 2-sided and 95% 1-sided CI estimation and adequate precision for estimation of standard deviation (SD) for numerical scales, i.e. allows for a sufficiently precise x 1.1 inflation factor for >80% 1-sided CI estimation of the SD. 47

Nested Qualitative Study Sample Size

The sample size in the nested qualitative component (participants with stroke SNMES n=12, participants with stroke control n=8 caregivers n=10, clinicians n=10) was based on recent research around code and meaning saturation in qualitative research for semi-structured interviews and focus groups. The sample size will be adequate to reach data and meaning saturation.

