2.3. Outcome measures/endpoints

Feasibility and feasibility measurement

As this is a feasibility study the primary outcomes of interest relate to aspects of feasibility and acceptability. A red, amber, green (RAG) system will be used to identify if the feasibility study should progress to a definitive trial. Section 7.3 Statistical Analysis Plan specifies the RAG system in more detail. The aspects of feasibility and acceptability that will be explored are:

STIM-STROKE Protocol v1.0 30-04-2025

IRAS ID: 332116 Page **18** of **70**

- 1. Interviews with people with stroke and their caregivers as well as focus groups with clinicians to explore their experiences and views about the acceptability of the SNMES intervention. Furthermore exploring/tracking adverse events and adverse reactions to treatment with SNMES (a common side effect of electrical stimulation is skin irritation from the electrode pads) will contribute to the determining the feasibility and acceptability of the intervention.
- 2. Study enrolment rates and screening (the number of patients who agree to take part of those eligible). Where possible reasons for not taking part will be recorded to help plan the definitive trial. Additionally. data will be collected on the time duration between hospital admission and randomisation.
- 3. Through a participant diary, records within the electrical stimulation machine, and participant/caregiver interviews we will estimate engagement with the protocol and explore reasons for low or non-engagement with the protocol/not achieving recommended dose. This will help the team to identify if the suggested dose is feasible and acceptable on a larger scale.
- 4. Through participant/caregiver interviews, therapist focus groups, and completeness of collected data explore the feasibility and acceptability of the outcome measures used. Acceptability of candidate outcomes measures and their variability to inform the selection of outcomes, including the primary outcome, for a definitive trial, likely to be the 10-Metre Walk Test.
- 5. The data collected (including those from the outcome measures and participant interviews, data completeness, and standard deviation estimates) will inform the sample size considerations and primary outcome measure for the definitive trial.

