7.2. Planned recruitment rate

The combined stroke admissions from both hospital sites are around 2000 strokes per year and 35% are likely to be eligible for this study. For example, UHD has around 1171 stroke admission per year. Of the 1171 admissions from Sept 2021-Aug 2022, 298 had a NIH lower limb motor score of 3 or 4, meeting our inclusion criteria (NIH lower limb motor score of ≥3). It is estimated around 50% of patients will be eligible as around 46% of people are not able to walk within 5 days after stroke which meets our inclusion criteria.

Around 149 people after stroke will be approached to join the study over the recruitment period. The team estimates it will be feasible to recruit 2-3 patients monthly over 12- months meeting the recruitment target. We have built in a two-month contingency for recruitment, if needed.

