Qualitative data from participants with stroke, caregivers, and clinicians will be analysed separately and where appropriate, we will synthesise experiences ensuring the recognition of the respective group voices. Findings will be mapped to the TFA and be used to inform study strategies for facilitating recruitment, retention, adherence and communication in a future trial.

Feasibility progression criteria

RAG (Red/amber/green) progression criteria ⁵⁰ will be used to assess the key feasibility objectives of recruitment, intervention adherence and retention to inform whether a main trial is possible and whether aspects of the design or other issues need modification in order to conduct the research successfully (Table 3).

Process data will be used to describe interpreted timelines to identify "fixable", "manageable" and "insurmountable" challenges to site opening, training, data collection and intervention fidelity, with regard to both the future main trial and clinical implementation in the event of a positive trial.

Table 3 RAG Criteria for Study Progression

STIM-STROKE Protocol v1.0 30-04-2025

IRAS ID: 332116 Page **55** of **70**

Outcome Green		Amber	Red
	(feasible with minimal or no modifications)	(feasible with moderate modification)	(major modification required, limited feasibility)
Recruitment	≥ 50 participants	30-49 participants	< 30 participants
(target n=60) Incomplete follow up	< 20%	20-40%	>40%
at 6 months Intervention	≥75%	50-75%	<50%
adherence	(≥27 sessions completed)	(18-26 sessions completed)	(<18 sessions completed)

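### Section 7.1 rests n = 60 on an uptake margin that does not describe the design and on an SD claim that makes no allowance for loss to follow-up

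*Protocol*

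**What the plan says.** Protocol section 7.1 opens with "We intend to recruit 60 participants with stroke over 12-months across two hospital sites" and gives two reasons for that number; the trial summary repeats them.

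- **Uptake:** "recruitment uptake to a 10% margin of error for 90% 2-sided and 95% 1-sided CI estimation". No expected uptake rate and no denominator are given.
- **SD of numerical scales:** a "sufficiently precise x 1.1 inflation factor for >80% 1-sided CI estimation of the SD". No loss to follow-up is mentioned.

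Other sections bear on both reasons:

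- Section 2.3 defines the enrolment rate as "the number of patients who agree to take part of those eligible".
- Section 7.2 expects that "Around 149 people after stroke will be approached to join the study over the recruitment period".
- Section 7.3, Table 3, has a progression criterion headed "Incomplete follow up" at 6 months: below 20% is Green, 20–40% is Amber. Recruitment is Green from 50 participants.
- Section 5.9 states that withdrawals after randomisation are not replaced.
- Section 7.3 uses the observed variability to size the definitive trial. Sections 2.3 and 5.6 point to the 10-Metre Walk Test as its primary outcome. Table 2 schedules that test only at 12 weeks and 6 months.

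**The concern.** A precision-based justification should let the reader go from the stated precision to the stated number. Here the uptake margin appears to have been worked out with the 60 recruits as the denominator, although under the protocol's own definition they are the numerator. The SD statement treats all 60 as measured, although the progression criteria accept substantial loss.

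The SD is the figure carried forward. If 1.1 is applied as an upper bound with more than 80% confidence when fewer than about 50 people were measured, the definitive trial is sized on a bound weaker than described. The 10-Metre Walk Test is the most exposed: it has no baseline value, so its SD comes wholly from people seen at follow-up.

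**Working it through.** **Inputs.** n = 60 and z = 1.645 (90% two-sided, 95% one-sided) from 7.1; 149 approached from 7.2; loss bands and the Green recruitment limit from 7.3, Table 3. The uptake rate is not stated. I use 60/149 = 40.3%, which the protocol implies, and a range of 30–50%.

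**1. Uptake, trying to reproduce 60.** n = p(1 − p)(1.645/0.10)²

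- p = 0.50: n = 68
- p = 0.403: n = 66
- p = 1/3: 2.706 × 0.222/0.01 = 60.1
- p = 0.30: n = 57

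Conversely, with 60 as the denominator, 1.645√(p(1 − p)/60) is 10.6 points at 50%, 10.4 at 40% and 9.7 at 30%. The stated margin and the stated number agree only near p = 1/3, which the protocol does not give and which differs from its own 60/149.

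**2. Uptake on the defined denominator.** 1.645√(0.403 × 0.597/149) = 0.066, so 40.3% ± 6.6 points (33.7 to 46.9%). The Wilson interval is 33.9 to 47.0% and Clopper–Pearson 33.5 to 47.3%.

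More generally, if 60 are recruited the denominator is 60/p and the margin is 1.645√(p²(1 − p)/60). Its maximum, at p = 2/3, is 8.2 points.

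**3. SD.** The 80% upper-limit factor is √(df/χ²₀.₂₀,df). The confidence attached to 1.1 is P(χ²_df ≥ df/1.21). Ranges cover df = n − 1 (a single SD) and df = n − 2 (pooled over two arms).

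| Measured | How reached | Factor at 80% | Confidence at ×1.1 |
|---|---|---|---|
| 60 | no loss | 1.089–1.090 | 82.4–82.7% |
| 50 | 10 of 60 lost | 1.100–1.101 | 79.8–80.1% |
| 48 | 20% of 60 lost | 1.102–1.103 | 79.3–79.6% |
| 40 | 20% of 50 lost | 1.114–1.116 | 76.7–77.0% |
| 36 | 40% of 60 lost | 1.121–1.124 | 75.2–75.6% |

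The claim is reproduced at 60. The smallest number that keeps it is 50 (single SD) or 51 (pooled), which is a loss of 10 or 9 people (17% or 15%).

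**4. Consequence for the definitive trial.** For a comparison of means, sample size scales with the SD squared. Using 1.1 where the 80% factor is 1.124 understates the size by (1.124/1.1)² − 1 = 4.4%. Where it is 1.103, the shortfall is (1.103/1.1)² − 1 = 0.5%.

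**The case against.** The strongest reply is that nothing promised is lost. Uptake will be estimated more precisely than ±10 points whatever the rate, and the SD statement is true for 60 measured people with slack for 9 or 10 losses. At 20% loss the shortfall is less than one percentage point of confidence. Several scales are also measured at baseline, where follow-up loss does not apply. All of this stands, and it limits the point to a correction of the stated justification.

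It is also fair that 149 is not a settled denominator. It equals 50% of 298, a count from one hospital, whereas 7.2 also says 35% of about 2000 admissions are likely to be eligible, which is 700. On 700, uptake would be 60/700 = 8.6% with a margin of about ±1.7 points. This does not rescue the 10%: neither denominator produces it.

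Three stronger readings are tempting, and the document does not support them.

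- **That 60 recruits fail to give the claimed uptake precision.** They exceed it; the margin cannot pass 8.2 points.
- **That any Green result breaks the SD claim.** With 60 recruited, Green allows at most 11 losses, leaving 49 measured and 79.6–79.8% confidence. The figure falls to about 77% only when recruitment is also near its Green limit of 50.
- **That the adherence criterion is under-powered.** Section 7.1 claims no precision for adherence, and Table 3 expresses it in sessions ("≥27 sessions completed" for Green), so there is no stated figure to correct.

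**Conclusion.** The point holds as a correction of the sample-size statement. The 10% margin is a mis-derived basis for 60: the design gives about ±6.6 points if 149 are approached, and 60 as a denominator gives 10.4–10.6 points at 40–50% uptake. The SD claim is correct without loss and down to 50 or 51 measured. It is slightly short at 48 (79–80%) and clearly short at 40 (77%) and 36 (75%), numbers that the Green and Amber limits allow.

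This assumes normally distributed scales and an SD from both arms together. The 10-Metre Walk Test may fare worse than the loss percentages suggest. Participants enter unable to walk or transfer independently, and those still unable to walk may give no timed value. The protocol gives no estimate of how many, so I put no figure on it.

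Nothing here shows that 60 is too few for a feasibility study.

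**What to change.** Keep n = 60 and rewrite the quantitative paragraph of 7.1 and its copy in the trial summary.

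1. State the uptake denominator and its margin: about ±6.6 points at 90% confidence if 149 are approached. First reconcile 149 with the 35% of about 2000 admissions in 7.2, and say whether it covers one site or both.
2. State the SD factor at 80% one-sided confidence by number measured: 1.09 at 60, 1.10 at 48 and 1.12 at 36–40.
3. Commit to the factor for the number actually measured when sizing the definitive trial. For the 10-Metre Walk Test, that is the number with a timed value.

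The cost is one paragraph in two places and slightly less favourable SD figures. No recruitment target, progression threshold or analysis changes. To keep 1.1 at 80% by recruitment instead would take 63–64 participants at 20% loss or 84–85 at 40% (50/0.8 to 51/0.8, and 50/0.6 to 51/0.6, rounded up); a feasibility study does not need that.
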